1. SYNOPSIS

Protocol Title: Effectiveness and Safety of Tenofovir Disoproxil Fumarate (TDF) in Chronic Hepatitis B Patients: A 3-Year, Prospective, Real-World Study in China

Short Title: Three-Year Effectiveness and Safety of TDF in Chinese CHB patients in real world

Rationale: Chronic infection with hepatitis B virus (HBV) represents a major global public health problem. It is estimated by WHO that around 257 million people are living with HBV infection. Chronic HBV infection leads to an increased risk of cirrhosis, hepatic decompensation, hepatocellular carcinoma (HCC), and liver-related premature mortality. HBV infection is particularly important in the Asian-Pacific region and China. Tenofovir disoproxil fumarate (TDF) was approved for the treatment of Chronic Hepatitis B (CHB) in the U.S. in 2008 and in China in 2013 based on Phase III clinical trials results. Since launching in China in 2014, the treatment experience of TDF is limited due to poor access. One important reason was the lack of real world evidence on long-term effectiveness and safety of TDF among Chinese CHB patients to guide clinical practice. The generation of real-world evidence from this study will provide clinical guidance to Chinese healthcare care professional (HCPs), address their concerns, and aid public health decision making on resource allocation.

Objectives and Research Questions:

Objectives	Research Questions
Objectives Primary Objective To assess the effectiveness among overall and sub-group Chinese CHB patients who receive TDF treatment in real-world	Among the overall analysis population and relevant sub-group* populations: Proportion of patients who achieve complete virologic response (CVR) at weeks of 48, 96, and 144. Proportion of patients who achieve HBeAg loss and/or HBeAg. seroconversion in HBeAg positive patients at weeks of 48, 96 and 144. Proportion of patients who achieve HBsAg loss and/or HBsAg seroconversion at
	 weeks of 48, 96 and 144. Proportion of patients who achieve transaminase normalization at weeks of 48, 96 and 144. Time to CVR, defined as time from

Objectives	Research Questions
	applicable)
Secondary Objective	
To assess the renal function change among overall and sub-group CHB patients during TDF	Among the overall analysis population and relevant sub-group* populations:
treatment	 Proportion of patients whose eGFR decline >20% from baseline at weeks of 48, 96, and 144.
	 Percentage of change from baseline in eGFR at weeks of 48, 96, and 144
	 Change from baseline in eGFR values at weeks of 48, 98 and 144
	 Proportion of patients with confirmed serum phosphate Grade 3 or 4 abnormality (<2.0 mg/dL) at weeks of 48, 98 and 144.
	 The percentage of change from baseline in serum phosphate at weeks of 48, 98 and 144.
	Change from baseline in phosphorus values at weeks of 48, 98 and 144

Overall Design: This is a China-based multi-centre, prospective, longitudinal, non-interventional study conducted in a real-world setting. This study will take a naturalistic approach, capturing real world medical practice and patient outcomes. Patients with diagnosed CHB will be recruited from general and specialized hospitals, where patients will receive medical care according to their physicians' standard practice without interventions and procedures. Patients will only be approached for participation after their treatment decision is made naturally at hospital visit. As per CHB treatment guideline, patients on anti-viral treatment will need to be monitored at least every 6 months in terms of therapy response, drug-related side effect and disease progression. The minimal essential lab test in line with routine clinical practice requested by CHB management guideline will be performed in central lab. Patient data will be collected using an innovative electronic approach (i.e. Smartphone APP) from routine lab tests, medical records, and investigators' evaluation at the entry of this study and at 6-month intervals thereafter for 3 years.

Number of Participants: Approximately 2000 CHB patients who newly initiate TDF and who already started TDF prior to entry of study will be recruited from general and specialized hospitals across China.

Treatment Groups and Duration: The recruited 2000 TDF-treated CHB patients will be followed up to 3 years as treatment group to evaluate the effectiveness of safety of TDF in real-world setting in China.

2017N314002_00 **CONFIDENTIAL** 207667

2. SCHEDULE OF ACTIVITIES (SOA)

The exact timing of each assessment is listed in the Schedule of Activities Table 1

Table 1 Schedule of Activities

	Patients who have started TDF prior to entry of study Patients who newly initiate TDF								
Procedure			newly initiate	Follow-up data collection period (3 years) ⁶					
	Initiation of TDF treatment	Entry of study	Entry of study	6 months	12 months	18 months	24 months	30 months	36 months
Informed consent		Χ	Χ						
Inclusion and exclusion criteria		Χ	X						
Baseline assessments ¹									
Sociodemographic		Χ	X						
Health behaviour		Χ	X						
Physical examination		Χ	X						
Medical history	X	Χ	Χ						
Regular assessments ^{2,3}									
HBV serology	X	Х	Х	Χ	Х	Х	Х	Χ	Х
HBV DNA *	X	Х	Х	Χ	Х	Х	Х	Χ	Х
ALT and/or AST	X	Χ	Х	Χ	Х	Х	Х	Χ	Х
Serum creatinine and eGFR [MDRD equation] *	Х	Χ	Х	Х	Х	Х	Х	Х	Х
Serum phosphate*	Х	Х	Х	Χ	Х	Х	Х	Х	Х
TDF treatment status or update	Х	Х	Х	Х	Х	Х	Х	Х	Х
Comorbidity and concomitant medication review	Х	Х	Х	Х	Х	Х	Х	Х	Х

	Ва	Baseline data collection⁵			F II				
Procedure	Patients who have started TDF prior to entry of study		Patients who newly initiate TDF		Follow-up data collection period (3 yea			s years)°	
	Initiation of TDF treatment	Entry of study	Entry of study	6 months	12 months	18 months	24 months	30 months	36 months
Patients adherence to TDF treatment		Χ		Х	Х	Х	Х	Х	Х
Other assessments ^{2,3}									
AFP		Χ	X	Χ	Х	Х	Х	Χ	Χ
Hepatic ultrasound		Х	Х	Х	Х	Х	Х	Х	Х
Genotype		Х	Х	Χ	Х	Х	Х	Х	Х
Bone mineral density (BMD)		Х	Х	Χ	Х	Х	Х	Х	Χ
Liver biopsy		Х	Х	Χ	Χ	Χ	Χ	Χ	Χ
Transient elastography		Х	Х	Χ	Х	Х	Х	Х	Х
computed tomography (CT) /magnetic resonance imaging (MRI)		Х	Х	Х	Х	Х	Х	Х	Х
Spontaneous AE/SAEs and pregna	ncy exposure d	lata collection4	•	•	•	•	•	•	•
Spontaneous AE/SAEs reporting		Х	Х	Χ	Χ	Х	Х	Χ	Χ
Pregnancy exposure reporting		Х	Х	Χ	Χ	Х	Х	Х	Χ

2017N314002_00 **CONFIDENTIAL** 207667

Abbreviations and notes:

AEs = Adverse events; CT= computed tomography; DNA = Deoxyribonucleic acid; eGFR = estimated Glomerular filtration rate; HBV = Hepatitis B virus; HBeAg = Hepatitis B envelope antigen; HCC = Hepatocellular carcinoma; MDRD = Modification of Diet in Renal Disease; MRI = Magnetic resonance imaging; SAEs = Serious adverse events AFP = Alpha feto protein * the essential lab test performed in central lab at or after entry of study

- 1. Sociodemographic: a brief baseline survey will be administered to collect a minimal amount of information. Additional study relevant information (only for enrolled patients) will be collected to enable study analyses.
- 2. Laboratory assessments and other clinical assessments: patients will only be monitored according to their physicians' standard practice without additional study-specified interventions and evaluations. Only available assessments will be collected from routine testing/evaluations using electronic approaches.
- 3. Assessments may not be conducted at the exact scheduled time intervals as there will be no intervention for patients' clinical care. Only available assessments will be collected from routine testing/evaluations. The schedule is to remind physicians to collect data regularly.
- 4. Adverse event and pregnancy exposure reporting: only spontaneous AEs/SAEs and pregnancy exposure related to any GSK products will be reported and summarized.
- 5. The baseline assessment filling with grey colure is mandatory and requested for baseline data collection.
- 6. Follow-up data collection period (e.g. months 6, 12, 18, 24, 30, 36) for patients who have started TDF before the entry of study will be anchored to their actual TDF initiation dates.

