6.1. Inclusion Criteria

Participants will be eligible to be included in this study only if all of the following criteria apply:

- 1. Male or female participants aged 12 years and above, at the time of signing the informed consent.
- 2. Participants who are diagnosed with CHB and meet the criterion of antiviral treatment for HBV infection judged by certified physicians.
- 3. Participants who newly initiate TDF ((only including brand TDF, Viread, and generic TDF, Beixin and Naxinde, which passed China generic quality consistency evaluation by Apr. 1 2018) monotherapy or combination therapy for the treatment of CHB by the judge of investigators at the study entry.
- 4. Participants who have already started TDF at the entry of study and will continue to be treated TDF (including brand TDF, Viread, and generic TDF, Beixin and Naxinde which passed China generic quality consistency evaluation by Apr. 01 2018) with essential medical information record and lab test reports available at the initiation of TDF treatment and follow-up visit.

Essential medical information record and lab test reports:

• *At the initiation of TDF treatment:*

- i. TDF treatment detail: TDF dose, brand name, start date;
- ii. Lab test (within +/-4 weeks of TDF treatment initiation): HBV DNA quantification (using high sensitive real-time PCR assays for HBV DNA quantification with lower limit of detection of 20IU/ml), ALT and/or AST, Serum creatinine and Serum phosphate, HBsAg/Anti-HBs and HBeAg/Anti-HBe
- iii. Medical information: CHB diagnosis and treatment history, co-morbidity, concomitant treatment
- The following visits under TDF treatment prior to entry of the study (At least once following visit record if TDF treatment >6 months):
 - i. Lab test: HBV DNA quantification (using high sensitive real-time PCR assays for HBV DNA quantification with lower limit of detection of 20IU/ml), Serum creatinine and Serum phosphate
 - ii. Medical information: co-morbidity, concomitant treatment, TDF treatment information

The proportion of patients who have already started TDF at the study entry will be monitored closely during study recruitment and will be kept less than 10% of the total study population.

- 5. Participants who are able to perform normal activities and seek regular medical care, e.g., willing to regularly perform lab test to monitor the treatment response.

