9.2. Populations for Analyses

The main population for analyses will consist of all consented participants who have the requested baseline data and at least one post-baseline assessment data.

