12. STUDY LIMITATIONS

This is a China-based multi-centre, prospective, longitudinal, non-interventional study conducted in a real-world setting in order to investigate long-term effectiveness and safety of TDF among Chinese CHB patients to guide clinical practice. The absence of comparison group is one of the major limitations to this study, which can be mitigated by a historical comparison leveraging previous trial data from literature or in-house alternatively. The mixing of the new initiator and on-treatment patients is another limitation, which may complicate the analysis due to varied treatment duration and inconsistent baseline information. Potential solutions include setting restriction on the inclusion criteria to the patients who have already started TDF prior to the entry of study in line with those of new initiators.

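### Patients already on TDF are pooled with new initiators on a clock that starts at their past TDF initiation, with no limit on prior duration: left-truncation (prevalent-user) selection and a weak renal baseline in up to 10% of the cohort

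*Protocol*

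**What the plan says.** - **Clock.** Section 2, note 6: the follow-up schedule (months 6 to 36) "for patients who have started TDF before the entry of study will be anchored to their actual TDF initiation dates".
- **Eligibility.** Section 6.1, criterion 4 admits "Participants who have already started TDF at the entry of study and will continue to be treated TDF". Prior use beyond 6 months triggers only a record requirement, "At least once following visit record if TDF treatment >6 months". No maximum is set. The share of such patients "will be kept less than 10% of the total study population".
- **Baseline for these patients.** The initiation values are specified as "Lab test (within +/-4 weeks of TDF treatment initiation", so a value taken after the first dose qualifies. Section 7.2 takes their earlier data from medical records. Under the Section 2 schedule, HBV DNA, creatinine/eGFR and phosphate are "the essential lab test performed in central lab at or after entry of study".
- **Analysis set.** Section 9.2 defines the main population as "all consented participants who have the requested baseline data and at least one post-baseline assessment data". Sections 9.3.2 and 9.3.3 summarise it as a whole and by subgroup. New versus prior TDF start is not a named subgroup; previous treatment with other NUCs is a different factor.
- **Acknowledgement.** Section 12 calls the mixing of the two groups a limitation, "which may complicate the analysis due to varied treatment duration and inconsistent baseline information". The remedy it offers is to align the entry criteria of the two groups.

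**The concern.** The two groups reach the analysis by different routes. A new initiator is observed from the first dose and is withdrawn on stopping TDF for at least 28 days (Section 8.2). A prior starter is observed only because he or she had not stopped by entry, yet is credited with all the time since initiation. Patients who stopped early for poor response, toxicity, cost or any other reason are present in one group and absent from the other.

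The record requirement adds a second asymmetry. A prior starter with more than 6 months of TDF brings a post-baseline HBV DNA, creatinine and phosphate result to enrolment and so already meets the main population's post-baseline condition. A new initiator can fail it.

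At stake are the week-48 and week-96 estimates, time to CVR, the duration and discontinuation summaries, and the renal results that the protocol wants in order to settle prescribers' safety concerns. Section 3.2 reports that eGFR loss on TDF is seen mainly early in treatment, which is the period a post-dose baseline can obscure.

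**Working it through.** **1. The protocol's precision figure.** Inputs from Section 9.1.2: N = 2,000, CVR 80%, 35% loss and discontinuation.

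- Completers: 2,000 × 0.65 = 1,300.
- Half-width: 1.96 × √(0.80 × 0.20 / 1,300) = 0.0217. The stated 2.2 points is reproduced.

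**2. New initiators only, with prior starters at the 10% cap.**

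- Completers: 1,800 × 0.65 = 1,170.
- Half-width: 1.96 × √(0.16 / 1,170) = 0.0229, or 2.3 points.

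**3. Weight of prior starters at week 144, at the cap (200 patients).** The protocol gives no separate drop-out rate for them, so two bounding assumptions are used.

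- Same 35% drop-out: 130 / (130 + 1,170) = 0.100.
- No drop-out: 200 / (200 + 1,170) = 0.146.

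**4. Shift in pooled CVR = weight × (prior-starter CVR − new-initiator CVR).** The gap is an assumption; the protocol gives no CVR by entry type.

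| Assumed gap | Shift, weight 0.100 | Shift, weight 0.146 |
|---|---|---|
| 0 points | 0 | 0 |
| 5 points | 0.5 | 0.7 |
| 10 points | 1.0 | 1.5 |

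At a 5% share the weights are 65/1,300 = 0.050 and 100/1,335 = 0.075, so a 10-point gap gives 0.5 to 0.75 points.

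**5. Where selection differs between the groups.**

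- *Week-48 or week-96 value, entry later.* A patient entering at month 30 supplies both values from records, conditional on still being on TDF at month 30. A new initiator's week-48 value carries no such condition.
- *Week-144 value, entry before week 144.* Stopping TDF is withdrawal (Section 8.2), missing values are generally not imputed (Section 9.3.5), and the precision is computed on completers. A patient counted at week 144 has stayed on TDF to week 144 in either group, so there is little difference in selection on persistence.
- *Week-144 value, entry after week 144.* The extra condition returns.
- *Discontinuation.* Time from initiation to entry contains no permanent stops, by construction. As an extreme case, suppose all 200 had at least 36 months of prior TDF and new initiators lost 35%: the pooled figure would be (1,800 × 0.35) / 2,000 = 630 / 2,000 = 31.5%.

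**6. How much of the schedule is prospective.** With m months of TDF at entry, 36 − m months of the anchored schedule remain: 24 for m = 12, 6 for m = 30, none for m of 36 or more. A patient with more than 3 years of prior TDF therefore contributes no prospective scheduled timepoint. Section 1 describes collection at entry and every 6 months thereafter for 3 years. TDF was launched in China in 2014 and criterion 4 refers to April 2018, so such patients can exist.

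**The case against.** The other side has several sound points.

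- **Small share, and disclosed.** Fewer than 10% are affected, the study is descriptive, and Section 12 names the mixing. This limits the importance. But Section 12 speaks of duration and baseline information, not of selection on persistence, and aligned entry criteria cannot bring back patients who stopped before entry.
- **CVR measurement is protected.** Criterion 4 requires a sensitive HBV DNA assay with a 20 IU/ml detection limit at initiation and follow-up, and a post-dose baseline does not change whether an undetectable level is reached. This stands. The baseline objection is confined to change-from-baseline measures.
- **A large CVR gap is not established.** A reader might infer that headline CVR is inflated by 1.0 to 1.5 points. That needs a gap of 10 points or more, which nothing in the protocol supports. Section 3.2 reports HBV DNA suppression above 89% among 3-year completers in cohorts newly started on TDF, so the gap among completers may be small.
- **Long prior use may be rare.** Access was poor after launch, and a full laboratory panel around initiation is required. This is fair: such patients are permitted, not shown to be common.
- **The RAP may deal with it.** Separate reporting or delayed entry may well be specified there, and their absence here is not itself an error. But eligibility, the time anchor, the baseline window and the main population are fixed in the protocol. No analysis plan can recover stoppers who were never enrolled or create pre-dose samples.

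**Conclusion.** The point holds as left-truncation (prevalent-user) selection combined with a weaker renal baseline, in fewer than 10% of patients. It matters most for week-48 and week-96 results when entry comes later, time to CVR, TDF duration and discontinuation, and change in eGFR and phosphate. The direction expected is toward longer persistence, fewer discontinuations and less renal decline.

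Two stronger readings are not supported. One is immortal-time bias: CVR before entry can be read from records, so patients are not event-free by construction. The other is a material distortion of week-144 CVR: on the completer basis that the protocol uses for its precision, both groups have persisted to that time unless entry came later.

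The CVR shift cannot be sized from the protocol. At the cap it is about 0.10 to 0.15 times the assumed gap, with those weights resting on 35% drop-out in new initiators and between 35% and none in prior starters. The renal effect cannot be sized either: the protocol does not say how much early change falls within the first 4 weeks, or how local and central results differ.

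**What to change.** 1. Make new initiators the primary population for the primary and secondary estimates. Report prior starters separately, and the pooled cohort as a sensitivity analysis.
2. In any pooled time-to-CVR analysis, keep TDF initiation as the origin but let prior starters enter the risk set at study entry. Leave out of the risk set those whose CVR is documented before entry. Simply ignoring pre-entry assessments would give them a falsely late CVR date.
3. For change from baseline in eGFR and phosphate, use only prior starters whose baseline samples are dated on or before the first TDF dose, and flag record-based against central values.
4. Add to criterion 4 a limit on prior TDF duration, so that at least the week-144 assessment is prospective. The ±28-day window opens at week 140 (144 − 4), so prior use shorter than 140 weeks at entry would do this.

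The cost is about 0.1 point of half-width (2.3 instead of 2.2, with 1,170 instead of 1,300 completers at the cap), slightly fewer eligible prior starters, and a short amendment to Sections 6.1, 9.2 and 9.3. No extra visits or tests are needed.

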3. INTRODUCTION

3.1. Background

Chronic infection with hepatitis B virus (HBV) represents a major global public health problem. It is estimated by WHO that around 257 million people are living with HBV infection (defined as hepatitis B surface antigen positive) [WHO HBV Face Sheet]. Chronic HBV infection leads to an increased risk of cirrhosis, hepatic decompensation, hepatocellular carcinoma (HCC), and liver-related premature mortality. In 2015, HBV infection accounted for 887 000 deaths, mostly from complications (including cirrhosis and hepatocellular carcinoma) [WHO HBV Face Sheet]. HBV infection is particularly important in the Asian-Pacific region and China. More than one-third of the world's chronic HBV carriers live in China. It is estimated that over half a million of Chinese people die annually from end-stage liver diseases. HBV infection and progression to end-stage disease is also associated with significant economic burden to the healthcare system and the society. Successful prevention of HBV infection and disease progression will considerably reduce humanistic sufferings and socioeconomic burden [Sun, 2010].

Over the past decades, five oral nucleoside/nucleotide analogues (NUCs) have been approved for antiviral treatment of chronic hepatitis B (CHB) including Tenofovir Disoproxil Fumarate (TDF), Entecavir (ETV), Telbivudine (LdT), Adefovir (ADV) and Lamivudine (LAM). It has been established that the risk of disease progression is decreased through the sustained reduction in HBV deoxyribonucleic acid (DNA) to undetectable levels. NUCs have been shown to effectively reduce serum HBV DNA and alanine aminotransferase (ALT) levels and therefore improve patients' hepatic reserve and liver histology. For NUCs, lifetime treatment is suggested for Chronic Hepatitis B (CHB) patients with advanced liver disease or in some instances with chronic Immunosuppressive therapy. The generally favourable side-effect profiles of the five NUCs demonstrated in registration trials coupled with the low rates of antiviral drug resistance with the newer agents make them attractive for use beyond 1 year.

However, infrequent but serious adverse events such as myopathy, neuropathy, and pancreatitis as well as renal impairment and reduced Bone Mineral Density (BMD) have been reported [Terrault, 2016]. NUCs-dependent nephrotoxicity was first observed in human immunodeficiency virus (HIV)-infected patients treated with adefovir (ADV) and primarily results in proximal tubular toxicity rather than glomerular toxicity, which was susceptible to the effects of mitochondrial toxicity [Fisher, 2001, Lampertico, 2016]. It was reported that proportion of patients with GFR-shifting from ≥ 90 to 60 - 89mL/min/1.73 m2 from baseline was 15%, 17.8% and 14.5% among LAM, ETV and TDF-treated non-cirrhotic compensated CHB patients respectively [Koklu, 2015]. However, HBV-infection, aging, comorbidity, e.g. hypertension, diabetes mellitus, is also linked to occurrence of chronic kidney disease in CHB patients besides NUC usage [Levey, 2012]. Hence, regular monitoring of renal function (including serum phosphate) as well as viral response is required in the management of CHB patients [Chinese Medical Association, 2015, Terrault, 2016, EASL, 2017]. Reduced BMD is another possible manifestation of renal toxicity due to renal proximal tubule damage leading to serum phosphate reduction and inadequate bone mineralisation [Kumar, 2012]. The

reported adverse effects of TDF on bone mineral density (BMD) are well known from its use in HIV treatment [Woodward, 2009].

